5. STUDY VARIABLES

5.1. Independent variables study object

The independent variables of the project are: a) belonging to the control or intervention group; and b) time, according to the timing of presurgical and postsurgical measurements. We also recorded as independent variables the general characteristics of the sample: age, BMI, sex, hours of weekly sports activity, orthopedic surgeon who performed the intervention and compliance with the program.

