2. STUDY DESIGN

An analytical, longitudinal, experimental, prospective, controlled and randomized clinical study will be conducted to analyze the cause-effect relationship of the Müller & Puig physiotherapy protocol under study in relation to the change in pain, functionality (modified Harris scale) and the range of mobility (ROM) in subjects surgically operated by Femoro-acetabular Impingement (FAI) by arthroscopy.

The study will be simple blind with blinded evaluator strategy with two parallel groups. The surgeons (recruitment) and assessors will be blinded with respect to the group belonging to the subject. The statistician will be blinded to the subjects group until the statistical analysis is completed. It is not possible to blind the physiotherapist who executes the treatment protocol or the study subjects. Subjects will be asked not to disclose their membership group or consult with the surgeon or the evaluator.

The randomization approach will be prepared by means of a randomization computer program, attributing a 1:1 ratio to the membership group. The interventionist physiotherapist will perform the randomization on the day of the first post-surgery physiotherapy session.

All participants will be informed of the purpose of the study through an information document prepared for this purpose and will be clarified any doubts that may arise. After answering as many questions as necessary, the subject must sign the informed consent document to be part of the study. The principles of the Declaration of Helsinki (2004) will

be respected at all times. The data collected will be treated confidentially by applying the current legislation on the protection of personal data (Organic Law 15/1999 of December 13, Protection of Personal Data) and / or any other applicable.

This study has been admitted by the Research and Ethics Committee of General University Hospital of Elche PI 6/2019.

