5.2. Dependent variables

The dependent variables of the study are the following:

Range of Mobility (ROM).

In the present study measurements will be made by goniometry of hip joint movement ranges. The goniometry is a technique of measurement of the angles created by the intersection of the longitudinal axes of the bones at the level of the joints.

These are continuous quantitative variables, measured in degrees with a range between 0° and 180°.

- a. ROM in hip flexion.
- b. ROM in hip extension.
- c. ROM in hip abduction.
- d. ROM in hip adduction.
- e. ROM in internal hip rotation.
- f. ROM in external rotation of the hip.

Orthopedic tests

The FAI will be checked through the performance of the Fabere, Fadir and Ober functional tests described below.

- a. **FABERE TEST:** The patient's hip is flexed, abducted and externally rotated by placing the external malleolus on the knee of the contralateral leg. The pelvis is

- stabilized and an overpressure is applied to the inside of the knee. It is positive if the pain in the buttock or groin is reproduced. Test with inter-evaluator reliability in Kappa values (95% CI) of 0.60.
- b. FADDIR TEST: Flexion, adduction and internal rotation test. The supine patient, the evaluator patiently brings the patient's hip up to 100° flexion and adduction while applying internal rotation. It is positive if pain in the groin is reproduced. Test with inter-evaluator reliability in Kappa values of 0.48.
 - c. OBER TEST: Patient in lateral decubitus position. The evaluator flexes the knee that is evaluated at 90° and abducts and extends the hip until it is level with the trunk. The evaluator lets the gravity bring the hip on adduction as possible. Test with inter-evaluator reliability of 0.90.

Variable intensity of pain

The Visual Analogue Scale (VAS) will be used. It is a continuous quantitative variable with a range between 0 and 10.

Evaluation functionality.

The modified Harris Scale will be used to the patient to evaluate the functionality of the hip and its interference in the activities of daily life. The patient will be evaluated with this scale prior to the surgical intervention and 14 weeks after the surgery.

6. STUDY GROUPS.

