The sample will be divided into 2 groups: Intervention Group and Control Group. The postoperative physiotherapeutic treatment protocol described will be applied to the intervention group. The non-intervention group will receive the nonspecific protocol of postoperative treatment for hip rehabilitation described by Gocen et al.

7. EVALUATION.

The evaluator is the person who will perform the pre and postsurgical measurements. He will be trained in the use of the goniometer and in the performance of orthopedic tests as well as in the material to be used. It will be located in the "Evaluation Room", with the material and conditions necessary to carry out the measurements. It will register and store the data for its later evaluation and statistical analysis.

The evaluator will be blinded with respect to the subject's belonging to the intervention or control group.

Data will be recorded at three times: before surgery, after 4 weeks and after 14 weeks of surgery. Immediate postoperative measurements will not be made, given that the clinical picture and tissue injury of the intervention could cause inaccurate results because a period of post-surgical wound stabilization has not elapsed.

These tests and measurements of variables will provide us with the degree of hip readjustment and its functionality, since they respond to the affected musculoskeletal structures both prior to the arthroscopy intervention due to the pathophysiology of the FAI, and after it for the wounds and surgical scars that are generated.

8. STUDY SEQUENCE.

A. Recruitment: it takes place before the surgery in the Traumatology clinic of Alicante Clinic (we attach authorization of the center to carry out the study) Two facultative specialists in orthopedic surgery and traumatology, transfer the information to the patient in written support about the characteristics of the study , purpose and form of follow-up, at the same time that they verify the eligibility of the subject according to the criteria of the study. Another member of the research team will independently check the eligibility of the subject in an evaluation session and will be responsible for performing the evaluations of the study variables before surgery, at 4 and 14 weeks after surgery. The evaluator will be present to resolve and clarify any doubts in this regard. After this, and with the acceptance of the patient to be part of the study, the informed consent will be signed.

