B. Pre-surgery evaluation: the Harris scale questionnaire modified prior to the surgical procedure will be completed. After signing the informed consent, the pre-surgical measurement will be carried out following the following sequence:

- Assessment tests of abduction, adduction, flexion, extension, internal rotation and external rotation ROM of the hip
- Next, the Ober, Fabere and Faddir muscle tests will be performed.
- Finally, the pain will be evaluated through the Visual Analog Scale (VAS)

C. Randomization: After the presurgical evaluation and following a simple randomization process by means of a computer program, the subjects are assigned to the control or intervention group.

D. Hip arthroscopy: The study subjects will receive adequate pre- and postoperative care including health education and exercise plan for the immediate postoperative period, in addition to a follow-up visit by the traumatologist after two weeks of the intervention.

E. Intervention: The subjects of the control group follow the general postsurgical treatment protocol described by Gocen et al. The subjects of the intervention group will perform a physiotherapy session of 45 minutes each one every two weeks for a total of 7 sessions (weeks 2, 4, 6, 8, 10, 12 and 14 post surgery) following the protocol described. In addition, they will have to follow a physiotherapy exercise plan at home whose compliance they will have to register in an activity diary to check adherence to treatment.

F. Post-surgery evaluation 1: The evaluation described in section B and C is repeated 4 weeks after surgery to subjects of both groups.

G. Post-surgery evaluation 2: The evaluation described in section B and C is repeated after 14 weeks of the surgery for the subjects of both groups, and the individual study is finished.

In both groups, it will be advised to avoid stairs, ramps, squats, forced hip flexion and legs crossing in all phases. The subjects that develop a deterioration in the Modified Harris scale or in the VAS at 4 weeks after surgery compared with the pre-surgical data or those subjects that reflect complications of the surgery will be evaluated again by their corresponding traumatologist to decide whether or not to remain in the program. All complications will be documented by the principal investigator. No adverse effects are expected.

Statistical Analysis Plan (SAP)

Size Sample and Feasibility

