- d. For the comparison of means between the results of both groups we will use the t-Student test of related samples and one-way ANOVA (when they are normal) or Mann-Whitney U test or Wilcoxon W test (when they do not meet the normal).
- e. Chi square test or ANCOVA to analyze the influence of the general characteristics of the sample on the effect of the intervention.
- f. For the reliability analysis of the measuring tools, Cronbach's alpha test will be used.
- g. Regression analysis using the multiple linear model to study the relationship between sets of variables.

A significance index of $p < 0.05$ will be established.

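### Item d of the SAP assigns no test to the between-group difference in change or to group-by-time, and its paired t test cannot compare the arms

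*Combined protocol and SAP*

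**What the plan says.** - **Question.** Protocol section 2 studies the physiotherapy protocol "in relation to the change in pain, functionality (modified Harris scale) and the range of mobility (ROM").
- **Factors.** Section 5.1 lists two main independent variables: group, and "b) time, according to the timing of presurgical and postsurgical measurements".
- **Readings.** Section 7: "Data will be recorded at three times: before surgery, after 4 weeks and after 14 weeks of surgery". For the modified Harris scale, section 5.2 is narrower: "The patient will be evaluated with this scale prior to the surgical intervention and 14 weeks after the surgery". Section 8 nevertheless repeats the evaluation at 4 weeks and acts on "The subjects that develop a deterioration in the Modified Harris scale or in the VAS at 4 weeks after surgery compared with the pre-surgical data".
- **Group comparison.** SAP, inferential analysis, item d: the "t-Student test of related samples and one-way ANOVA (when they are normal"), with Mann-Whitney U or Wilcoxon W as the non-normal alternatives.
- **Other methods listed.** Item e: "Chi square test or ANCOVA to analyze the influence of the general characteristics of the sample on the effect of the intervention". Item g lists multiple linear regression, with no outcome or terms stated.
- **Not stated.** The plan does not say whether item d is applied to raw scores or to change. It names no time point for the main comparison and gives no rule for missing readings.

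**The concern.** The design asks whether change over time differs between two randomised arms. The item that compares the arms names no method for that question. One of its two parametric tests, the related-samples t test, answers a different one: whether a single arm changed from one occasion to another. If it carries the conclusion, the likely form is improvement in one arm and none in the other, which is not evidence of a difference between arms. The other listed tests can compare arms, but as written they use neither the pre-surgical reading nor, for the 14-week comparison, the 4-week reading of a patient who has left.

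That last point has a concrete route here. Under section 8, patients who are worse at 4 weeks are re-evaluated for whether they stay in the programme, so absence at 14 weeks may depend on the 4-week result.

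**Working it through.** **1. What each listed method can do for this question**

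| Method (SAP item) | What it answers | Gap |
|---|---|---|
| Related-samples t test; Wilcoxon if used as its paired rank counterpart (d) | Change within one arm | Cannot compare independent arms |
| One-way ANOVA, Mann-Whitney (d) | Arm difference at one visit, or in change if change is the input | Input not stated; pre-surgical value not used if run on raw scores |
| ANCOVA (e) | Could adjust for the pre-surgical value | Assigned to sample characteristics |
| Multiple linear regression (g) | Could hold group, time and baseline terms | No outcome or terms given |

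**2. The plan's own figure.** The SAP gives around 30 subjects per group as a feasibility figure, without effect size or SD, so it cannot be reproduced. Back-solving (two-sided alpha 0.05 assumed, since sidedness is not stated; 80% power) gives d = (1.960 + 0.842) × √(2/30) = 0.72 SD, or 0.74 by the t distribution. I use 0.72 below as the difference that an unadjusted comparison detects with 80% power.

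**3. Separate paired tests, no true group difference.** With 30 per arm and the same standardised within-arm change dz in both, let p be the power of one paired test. The chance that exactly one arm is significant is 2p(1 − p).

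| dz (assumed) | p | 2p(1 − p) |
|---|---|---|
| 0.3 | 0.355 | 46% |
| 0.4 | 0.563 | 49% |
| 0.5 | 0.754 | 37% |
| 0.6 | 0.888 | 20% |

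At dz = 0.8 it falls to 2%, because both arms are then nearly always significant and the tests say nothing about the difference.

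**4. Value of the pre-surgical reading.** Power = Φ(d / (s√(2/30)) − 1.96) with d = 0.72. The SD factor s is 1 for the follow-up score alone, √(2(1 − ρ)) for change, and √(1 − ρ²) with baseline adjustment. The documents give no ρ; 0.3 to 0.7 is assumed.

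| ρ | Follow-up score only | Change score | Baseline-adjusted |
|---|---|---|---|
| 0.3 | 80% | 65.8% | 83.6% |
| 0.5 | 80% | 80.0% | 89.9% |
| 0.7 | 80% | 95.1% | 97.5% |

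**5. Loss that depends on the 4-week result.** No drop-out rate is given, so this is an example. Suppose 20% of controls are lost, all from the worse half at 4 weeks (mean −0.80 SD), no intervention patients are lost, the 4-to-14-week correlation is 0.6, and there is no true effect. The bias among those remaining is (0.2 × 0.80 / 0.8) × 0.6 = 0.12 SD. If the intervention arm loses 10% in the same way, subtract (0.1 × 0.80 / 0.9) × 0.6 = 0.05, leaving 0.07 SD. With equal loss it is zero. In simulation, a model using the 4-week score had bias of about zero in the 0.12 SD case.

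**6. Precision from the 4-week data of drop-outs.** At 20% drop-out in both arms, baseline-adjusted power with and without those readings is 75.2% vs 74.8% (ρ = 0.3), 83.3% vs 82.5% (0.5) and 94.6% vs 93.9% (0.7). The gain stays under 1.5 points up to 30% drop-out.

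**The case against.** The strongest reply is that the listed tests can give a valid answer. In a randomised trial, a one-way ANOVA or Mann-Whitney test at 14 weeks is a sound test of the effect. Run on change from baseline, it is equivalent to the group-by-time test for those two occasions. ANCOVA and regression are also in the list. This stands: the question is not untestable, and it would be wrong to say that every listed test is one-factor or two-sample. What remains is that the plan does not say which of these it will do, and that it offers a within-arm test for a between-arm comparison.

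Three stronger readings are tempting but unsupported:

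- **Repeated readings pooled as independent.** Pooling would inflate type I error. From 2(1 − Φ(1.96/√(1 + (k − 1)ρ))), it would be 8.6% to 13.3% for two readings and 12.1% to 20.6% for three, at ρ of 0.3 to 0.7. But the plan nowhere proposes pooling, and listing a related-samples test suggests that pairing was in view.
- **Patients absent at 14 weeks lose their 4-week data.** Visit by visit, they still count in the 4-week comparison; only the 14-week comparison ignores that reading. Completer-only analysis is itself an inference from silence.
- **Serious bias from drop-out.** The 0.12 SD example assumes loss in one arm only. It is about 0.43 standard errors (0.12/0.276) and would take a 5% type I error to about 7%.

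**Conclusion.** The point holds as a gap in specification plus one misassigned test. No method in item d is assigned to the between-group difference in change or to group-by-time, and the related-samples t test cannot compare the arms. Relying on separate paired tests would be the most damaging choice: about 20% to 49% of null trials would show exactly one significant arm, assuming dz between 0.3 and 0.6.

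The main gain from changing the analysis is baseline adjustment: power of 83.6% to 97.5% where the unadjusted test has 80%, for ρ between 0.3 and 0.7. Protection against loss linked to the 4-week result is a second, smaller reason. It is plausible under section 8, but its size is unknown. Extra precision from the 4-week data of drop-outs is negligible and should not be used as an argument. The plan should be changed here, but a visit-by-visit ANOVA or rank test would not be invalid.

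**What to change.** For VAS, each of the six ROM measures and the modified Harris scale, replace the paired t test and one-way ANOVA in item d, as the between-arm analysis, with a linear mixed model per outcome. Include group, visit, group-by-visit and the pre-surgical value, with unstructured within-patient covariance and all available readings. Report the between-arm difference with 95% CI at 14 weeks (main) and at 4 weeks. Keep paired tests as within-arm description only. Keep a rank test as a sensitivity analysis if residuals are clearly non-normal.

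Where an outcome has only pre-surgical and 14-week readings, the model reduces to ANCOVA and there is no 4-week reading to help with losses. Whether this applies to the modified Harris scale is unclear: sections 5.2 and 8 conflict on a 4-week reading and must be reconciled. The Fabere, Faddir and Ober tests are outside this model and need their own stated method.

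The cost is SAP wording and slightly more analysis, with no new data. The downside is a missing-at-random assumption, which is weaker than what a completer-only 14-week comparison would require.

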5.2. Dependent variables

The dependent variables of the study are the following:

Range of Mobility (ROM).

In the present study measurements will be made by goniometry of hip joint movement ranges. The goniometry is a technique of measurement of the angles created by the intersection of the longitudinal axes of the bones at the level of the joints.

These are continuous quantitative variables, measured in degrees with a range between 0° and 180°.

- a. ROM in hip flexion.
- b. ROM in hip extension.
- c. ROM in hip abduction.
- d. ROM in hip adduction.
- e. ROM in internal hip rotation.
- f. ROM in external rotation of the hip.

Orthopedic tests

The FAI will be checked through the performance of the Fabere, Fadir and Ober functional tests described below.

- a. **FABERE TEST:** The patient's hip is flexed, abducted and externally rotated by placing the external malleolus on the knee of the contralateral leg. The pelvis is

- stabilized and an overpressure is applied to the inside of the knee. It is positive if the pain in the buttock or groin is reproduced. Test with inter-evaluator reliability in Kappa values (95% CI) of 0.60.
- b. FADDIR TEST: Flexion, adduction and internal rotation test. The supine patient, the evaluator patiently brings the patient's hip up to 100° flexion and adduction while applying internal rotation. It is positive if pain in the groin is reproduced. Test with inter-evaluator reliability in Kappa values of 0.48.
 - c. OBER TEST: Patient in lateral decubitus position. The evaluator flexes the knee that is evaluated at 90° and abducts and extends the hip until it is level with the trunk. The evaluator lets the gravity bring the hip on adduction as possible. Test with inter-evaluator reliability of 0.90.

Variable intensity of pain

The Visual Analogue Scale (VAS) will be used. It is a continuous quantitative variable with a range between 0 and 10.

Evaluation functionality.

The modified Harris Scale will be used to the patient to evaluate the functionality of the hip and its interference in the activities of daily life. The patient will be evaluated with this scale prior to the surgical intervention and 14 weeks after the surgery.

6. STUDY GROUPS.

The sample will be divided into 2 groups: Intervention Group and Control Group. The postoperative physiotherapeutic treatment protocol described will be applied to the intervention group. The non-intervention group will receive the nonspecific protocol of postoperative treatment for hip rehabilitation described by Gocen et al.

7. EVALUATION.

The evaluator is the person who will perform the pre and postsurgical measurements. He will be trained in the use of the goniometer and in the performance of orthopedic tests as well as in the material to be used. It will be located in the "Evaluation Room", with the material and conditions necessary to carry out the measurements. It will register and store the data for its later evaluation and statistical analysis.

The evaluator will be blinded with respect to the subject's belonging to the intervention or control group.

Data will be recorded at three times: before surgery, after 4 weeks and after 14 weeks of surgery. Immediate postoperative measurements will not be made, given that the clinical picture and tissue injury of the intervention could cause inaccurate results because a period of post-surgical wound stabilization has not elapsed.

These tests and measurements of variables will provide us with the degree of hip readjustment and its functionality, since they respond to the affected musculoskeletal structures both prior to the arthroscopy intervention due to the pathophysiology of the FAI, and after it for the wounds and surgical scars that are generated.

8. STUDY SEQUENCE.

A. Recruitment: it takes place before the surgery in the Traumatology clinic of Alicante Clinic (we attach authorization of the center to carry out the study) Two facultative specialists in orthopedic surgery and traumatology, transfer the information to the patient in written support about the characteristics of the study , purpose and form of follow-up, at the same time that they verify the eligibility of the subject according to the criteria of the study. Another member of the research team will independently check the eligibility of the subject in an evaluation session and will be responsible for performing the evaluations of the study variables before surgery, at 4 and 14 weeks after surgery. The evaluator will be present to resolve and clarify any doubts in this regard. After this, and with the acceptance of the patient to be part of the study, the informed consent will be signed.

B. Pre-surgery evaluation: the Harris scale questionnaire modified prior to the surgical procedure will be completed. After signing the informed consent, the pre-surgical measurement will be carried out following the following sequence:

- Assessment tests of abduction, adduction, flexion, extension, internal rotation and external rotation ROM of the hip
- Next, the Ober, Fabere and Faddir muscle tests will be performed.
- Finally, the pain will be evaluated through the Visual Analog Scale (VAS)

C. Randomization: After the presurgical evaluation and following a simple randomization process by means of a computer program, the subjects are assigned to the control or intervention group.

D. Hip arthroscopy: The study subjects will receive adequate pre- and postoperative care including health education and exercise plan for the immediate postoperative period, in addition to a follow-up visit by the traumatologist after two weeks of the intervention.

E. Intervention: The subjects of the control group follow the general postsurgical treatment protocol described by Gocen et al. The subjects of the intervention group will perform a physiotherapy session of 45 minutes each one every two weeks for a total of 7 sessions (weeks 2, 4, 6, 8, 10, 12 and 14 post surgery) following the protocol described. In addition, they will have to follow a physiotherapy exercise plan at home whose compliance they will have to register in an activity diary to check adherence to treatment.

F. Post-surgery evaluation 1: The evaluation described in section B and C is repeated 4 weeks after surgery to subjects of both groups.

G. Post-surgery evaluation 2: The evaluation described in section B and C is repeated after 14 weeks of the surgery for the subjects of both groups, and the individual study is finished.

In both groups, it will be advised to avoid stairs, ramps, squats, forced hip flexion and legs crossing in all phases. The subjects that develop a deterioration in the Modified Harris scale or in the VAS at 4 weeks after surgery compared with the pre-surgical data or those subjects that reflect complications of the surgery will be evaluated again by their corresponding traumatologist to decide whether or not to remain in the program. All complications will be documented by the principal investigator. No adverse effects are expected.

Statistical Analysis Plan (SAP)

Size Sample and Feasibility

The statistical program that we will use will be SPSS v.20. To determine the sample size, a pilot study will be conducted with the same methodology as the original study to a group of 10 subjects. These subjects will be assigned to the same group. This pilot study will provide us with the estimates of the mean and variance of the response variable, thus being able to calculate the appropriate sample size by determining a minimum power value of 80% ($W > 80\%$) and a confidence level of 95% ($p < 0.05$).

The pilot sample will be part of the final sample to be studied if there are no changes in the protocol or in the variables to be measured.

The FAI is an important cause of coxarthrosis. Hip osteoarthritis is a pathology of high prevalence, with important socioeconomic repercussions. In Spain, 16% of the population over 20 years of age suffers, with a clear prevalence in women.

In a retrospective radiological study, Marín et al found around 70% the presence, on radiographs performed years before the intervention, of femoral and acetabular signs suggestive of femoroacetabular shock in children under 55 years who underwent total arthroplasty of hip. Other authors have reported values around 45% in patients pending intervention of hip prostheses with an age range between 30 and 82 years.

We consider it feasible to obtain a sample necessary for the present study (around 30 subjects per group) in view of the sample size of published articles on the effectiveness of conservative or postoperative treatment protocols for hip disorders and FAI and the high prevalence of FAI. The estimated time of obtaining the necessary sample will be around 6 months.

Descriptive analysis: A descriptive statistical analysis of all the variables will be carried out using frequency tables for the qualitative variables, and the minimum, maximum, average and standard deviation for the quantitative variables.

Inferential analysis: In relation to the inferential analysis, the statistical tests described below will be performed.

- a. Normal distribution test of Kolmogorov-Smirnov to identify the distribution of the samples.
- b. Levene test to check if the variances are homogeneous.

- c. ANOVA test (when the sample were are normal) or Kruskal-Wallis test (when it do not comply with normality) to check the homogeneity of the characteristics of the subjects between the different groups before the intervention.
- d. For the comparison of means between the results of both groups we will use the t-Student test of related samples and one-way ANOVA (when they are normal) or Mann-Whitney U test or Wilcoxon W test (when they do not meet the normal).
- e. Chi square test or ANCOVA to analyze the influence of the general characteristics of the sample on the effect of the intervention.
- f. For the reliability analysis of the measuring tools, Cronbach's alpha test will be used.
- g. Regression analysis using the multiple linear model to study the relationship between sets of variables.

A significance index of $p < 0.05$ will be established.

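### VAS pain is rated last, after pain-provoking hip tests and with no rest interval or reference period stated, so it can mix the patient's own pain with pain from the examination

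*Combined protocol and SAP*

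**What the plan says.** Section 8B, Pre-surgery evaluation, presents the assessment as a fixed order: "the pre-surgical measurement will be carried out following the following sequence". The steps are:

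1. "Assessment tests of abduction, adduction, flexion, extension, internal rotation and external rotation ROM of the hip"
2. "Next, the Ober, Fabere and Faddir muscle tests will be performed"
3. "Finally, the pain will be evaluated through the Visual Analog Scale (VAS"

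Section 8F carries this forward: "The evaluation described in section B and C is repeated 4 weeks after surgery to subjects of both groups". Section 8G does the same at 14 weeks. Both also refer to step C, but C is randomization, so the measurements being repeated are those in B.

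Section 5.2 describes the tests. Fabere includes an overpressure at the knee, and "It is positive if the pain in the buttock or groin is reproduced". For Faddir, "It is positive if pain in the groin is reproduced". Of the VAS, apart from naming it as the pain scale, it says only: "It is a continuous quantitative variable with a range between 0 and 10".

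Pain is one of the three outcomes in the general objective (section 1). Under section 8, worsening of the VAS from its pre-surgical value is also one of the grounds for reassessment by the traumatologist at 4 weeks.

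**The concern.** A positive Fabere or Faddir means that the evaluator has just reproduced the patient's pain. The next item in the list is a pain rating that does not say whether it refers to pain now, at rest, on activity, at worst, or averaged over some period. A patient could reasonably answer with the pain felt during or after the examination.

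Four things are at stake:

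- **Noise.** Response to provocation adds variance to the VAS.
- **Overlap.** The VAS and the orthopaedic tests are listed as separate dependent variables, but one can feed into the other.
- **Pre-post change.** If fewer tests are positive after surgery, part of the fall in VAS reflects the fall in positivity. If more are positive, the distortion runs the other way.
- **The 4-week check.** It compares two VAS values, each of which may carry a different provoked component.

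**Working it through.** **Reading check.** Four facts are needed, and all are in the text: the VAS comes last (8B); two of the three tests before it are defined by reproduced pain (5.2); the order recurs at both follow-up visits (8F, 8G); and no rest interval or VAS reference period appears in 5.2, 7 or 8. Nothing elsewhere softens this. The modified Harris questionnaire is listed ahead of the physical sequence in 8B, so the point is confined to the VAS.

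**Size.** The SAP's figure of around 30 per group cannot be reproduced. It rests on the size of published studies, and the mean and variance are left to the pilot. What follows is illustration on assumed values.

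*Scenario 1: provoked pain as pure noise.*

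Inputs from the SAP: 30 per arm, alpha 0.05 (two-sided assumed), power 80%.

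- Detectable difference, normal approximation: (1.960 + 0.842) × √(2/30) = 2.802 × 0.2582 = 0.723 SD.
- Assumption: provoked pain adds independent variation with SD equal to k times the SD of the patient's own pain. The total SD becomes √(1 + k²).
- Power = Φ(0.723 / [√(1 + k²) × 0.2582] − 1.960).

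| k (assumed) | Total SD | Power at 30 per arm | n per arm to restore 80%: 30 × (1 + k²) |
|---|---|---|---|
| 0 | 1.000 | 80% | 30 |
| 0.25 | 1.031 | 78% | 31.9, so 32 |
| 0.5 | 1.118 | 71% | 37.5, so 38 |

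Using the t distribution, the starting difference is 0.736 SD and the powers are 77.6% and 70.8%, which round to the same figures.

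If the VAS is the response variable used in the pilot calculation (the SAP does not name it), the extra variance would already be in the pilot SD. The cost would then appear as a larger sample, not as lost power.

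*Scenario 2: provoked pain as a shift in the mean.*

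Assume that a positive test adds 1 to 2 VAS points.

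- A 50-percentage-point fall in positivity after surgery adds 0.50 × 1 = 0.5 to 0.50 × 2 = 1.0 points to the apparent pre-post improvement.
- A 20-percentage-point difference in positivity between arms moves the group contrast by 0.20 × 1 = 0.2 to 0.20 × 2 = 0.4 points.

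*Why the scenarios should not be added.* Scenario 1 takes provoked pain to be unrelated to treatment. The between-arm part of scenario 2 takes it to depend on treatment. To see what happens if both are imposed, let the shift run in the direction of benefit and assume a VAS SD of 2 to 3 points. The shift is then 0.2/3 = 0.067 SD to 0.4/2 = 0.2 SD.

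- k = 0.25: (0.723 + 0.067)/1.031 = 0.766 SD gives 84%; (0.723 + 0.2)/1.031 = 0.896 SD gives 93%.
- k = 0.5: (0.723 + 0.067)/1.118 = 0.707 SD gives 78%; (0.723 + 0.2)/1.118 = 0.826 SD gives 89%.

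Most of these lie above 80%, so even the sign of the effect on power depends on the assumptions.

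**The case against.** The strongest reply is that the order is identical in both arms and at every visit, that the evaluator is blinded (section 7), and that the baseline measurement precedes allocation. This stands. A reader might infer that the order biases the comparison towards one arm, and the documents do not support that. If treatment has no effect, the provoked component has the same expectation in both arms, and the order creates no false difference. If treatment does change how the hip responds to provocation, the VAS picks up a real effect on irritability. The difficulty is then what the VAS measures. The reply does not answer the points on noise, overlap or pre-post change.

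A reader might also infer that contamination is certain. Section 8B gives order, not timing. It does not say that the rating follows immediately, that the ROM movements are taken to end range, or that briefly reproduced pain lasts until the rating. The text supports only that mixing can occur.

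Thirdly, a reader might treat the fall to 78% or 71% as an established loss of power. It is not: the noise ratios are assumed, and so is the difference of 0.72 SD, which is simply the value that gives 80% power at 30 per arm.

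Finally, the 4-week check leads to a reassessment, not to automatic withdrawal, and worsening on the Harris scale or surgical complications also trigger it. That limits the consequence. The VAS comparison feeding the check can still be contaminated, in a direction the documents do not settle.

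**Conclusion.** The concern holds as a weakness in how the pain outcome is measured. Following the plan as written can let examination-provoked pain into a named outcome, and nothing in the documents prevents it. It is not a demonstrated bias between arms. The size is unknown because the documents give no VAS mean, SD, test positivity or carry-over of provoked pain. The illustrative range of 80% down to 78% or 71% rests on independent noise of 0.25 to 0.5 SD, a two-sided test and 30 per arm. It shows a possible order of magnitude and does not set the severity. The case for acting is that the outcome becomes clearer at almost no cost.

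**What to change.** - In section 8B, and so in 8F and 8G, place the VAS before goniometry and before the Ober, Fabere and Faddir tests, in the same order at all three visits.
- In section 5.2, state the VAS reference period: which pain is being rated, and over what time. Reordering alone would leave the outcome undefined.
- Record pain provoked by the tests only as part of the test result.

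**Cost.** None if the change is made before the first pilot subject. If the pilot has begun, this is a protocol change. The SAP (Size Sample and Feasibility) keeps the 10 pilot subjects in the final sample only if neither the protocol nor the measured variables change. As that rule stands they could not be pooled, and flagging them in the dataset would not satisfy it. They are 10 of about 2 × 30 = 60 subjects, or 17%, so the change is best made before the pilot starts.
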